5.3 Dietary restrictions and smoking

■ [REDACTED]

■ [REDACTED]

- No alcohol for approximately 24 hours before the study visits until the Study Completion evaluation.
- No cigarettes/use of nicotine products are allowed on the study.
- No grapefruit or grapefruit juice is to be consumed for approximately 7 days prior to dosing until 7 days following the last dose.

■ [REDACTED]

■ [REDACTED]

While domiciled, subjects will be provided a standardized breakfast meal according to their randomization assignment below for Part A and B:

Part A: Effects of carbohydrate in the breakfast meal

- The breakfast meal will contain 600 calories providing 50% carbohydrate, 15% protein and 35% fat. This meal will be served at approximately 07.30, immediately after LIK066 administration. The breakfast meal should be consumed within 15 mins.
- The breakfast meals during each treatment period will include the following and according to the randomization assignment:
 - 600 calories - 50% carbohydrate, 15% protein, and 35% fat
 - 600 calories - 25% carbohydrate, 40% protein, and 35% fat
 - 600 calories - 0% carbohydrate, 65% protein, and 35% fat

Part B: Effects of supplements

- All breakfast meals in Part B treatment periods will include approximately 600 calories containing 50% carbohydrate, 15% protein, and 35% fat, and served at approximately 07.30 immediately after administration of LIK066, then the designated supplements (psyllium, calcium carbonate or no supplement) according to randomization.

In both study parts and during each treatment period, lunch will be served at approximately 13.00 (after completion of the PD sample collection and at least 5 hours from breakfast), and dinner will be served at approximately 18.30. The timing of meals should be harmonized on all days (Day -1, Day 3, Day 11, and Day 19) when PD are measured to minimize the effects of diurnal rhythm. A snack may be served at approximately 20.00 if needed.

Lunch and dinner meals will be provided as a menu option, and study participants can choose from the menu based on their usual eating habits.

Further details on the specified meals and potential meal menu options will be provided in the SOM.

A meal record will confirm timing and consumption of meal. A copy of the diet with content and nutritional information (e.g., amount of protein, sodium, carbohydrates, fat and calories for each meal) will be provided to the Sponsor upon request.

5.4 Other restrictions

- No strenuous physical exercise (e.g. weight training, aerobics, football) for 3 days before dosing until after Study Completion evaluation.
- During the domiciled period, study participants are encouraged to maintain usual activity level in the study site (e.g., light to moderate walking) to minimize altered bowel habits associated with inactivity.

6 Treatment

6.1 Study treatment

The investigational drug, LIK066, 50 mg tablets, will be prepared by Novartis and supplied to the Investigator as open labeled bulk medication. Supplements (Sugar Free version) including psyllium and calcium carbonate will be sourced by the Site.

Details on the requirements for storage and management of study treatment, and instructions to be followed for subject numbering, prescribing/dispensing and taking study treatment are outlined in the Site Operations Manual.

6.1.1 Investigational treatment and control drugs

	Formulation	Unit Dose	Packaging	Provided by
LIK066	Tablet	50 mg	Open-label, bulk, blister-pack	Novartis
Psyllium	Powder	6 grams 1 gram (4 mL	Over the counter	Sourced by site
Calcium carbonate	Liquid	equivalent sugar free formulation)	Over the counter	Sourced by site

6.1.2 Additional study treatment

No additional treatment beyond the investigational drug LIK066 and the supplements (psyllium and calcium carbonate) are included in this trial.

6.2 Treatment arms

Study treatments are defined as:

- A: Daily dose of 50 mg LIK066+50% carbohydrate
- B: Daily dose of 50 mg LIK066+25% carbohydrate
- C: Daily dose of 50 mg LIK066+0% carbohydrate
- D: Daily dose of 50 mg LIK066+50% carbohydrate+ 6 g psyllium
- E: Daily dose of 50 mg LIK066+50% carbohydrate+1g calcium carbonate (1 g calcium carbonate in 4mL liquid sugar-free formulation)

In each part of the study, subjects will be randomized to one of the following 3 treatment sequences in the ratio of 1:1:1.

Table 6-1 **Definition of treatment sequences**

Part A			
Sequence	Period 1	Period 2	Period 3
1	A	B	C
2	B	C	A
3	C	A	B

Part B			
Sequence	Period 1	Period 2	Period 3
4	A	D	E
5	D	E	A
6	E	A	D

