Subjects who meet the inclusion/exclusion criteria at screening will be admitted to the clinical site on Day -3. A survey for food preference of each subject will be conducted so that meal menus can be provided to accommodate the usual diet habits of each individual. As diet changes may impact on the bowel movement habits, subjects participating in this study will be encouraged to follow their usual dietary habit whenever possible.

During the baseline period, a standardized breakfast meal (600 calories with 50% carbohydrate, 15% protein and 35% fat) will be served; for lunch and dinner, menu options will be offered so that each subject can follow their usual diet following the standard nutritional guidance.

Starting on Day-3 and continuing through the 25 days of domiciling period, stool assessments will take place whenever a subject has a bowel movement ([Assessment schedule](#)). Starting from Day -2 at approximately 07.00, a 24-hour stool collection will be done for each subject. During Day -2 through Day 22, daily bowel movements will be monitored and collected, and stored in a refrigerated container and will be assessed by the study staff according to the Bristol Stool Chart and bowel movement record.

The stool assessments include recording of the timing, weight, pH, consistency of stool using Bristol Stool Chart, [REDACTED]

[REDACTED] according to the

[Assessment schedule](#).

Day -1 Baseline Assessment

Twenty-four (24) hour baseline stool samples will be collected from Day-1 to Day 1 morning (approximately 07.00 to 07.00) for various assessments of fecal parameters according to the [Assessment schedule](#).

[REDACTED]

On Day -1, at approximately 07.30, a 600 calorie standardized breakfast meal containing 50% carbohydrate, 15% protein, and 35% fat will be served, and subjects will drink 250 mL water immediately before breakfast during treatment periods. The time of drinking water will be defined as time zero for the measurement of baseline PD endpoints. Each subject will consume the designated breakfast within 15 mins. [REDACTED]

[REDACTED] Lunch will be served at approximately 13.00 (after completion of the PD sample collection and at least 5 hours from breakfast), and dinner will be served at approximately 18.30. The timing of meals should be harmonized on all days (Day -1, Day 3, Day 11, and Day 19) when PD are measured to minimize the effects of diurnal rhythm.

[REDACTED]

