Study subjects will also remain domiciled at the clinical site during the washout periods and no LIK066 will be administered. There are no particular restrictions for the meals during the washout time period, and subjects can choose foods according to their eating habits and preference (meal menu to be provided offering varied choices). The estimated calories consumed will be documented for each meal for each subject. As with the run-in and baseline period, all stool samples will be collected and bowel movement assessments will be recorded for every subject.

On Day 22, following the end of study assessments, subjects will be discharged from the clinical site.

During the study, safety assessments will include physical examinations, vital signs, standard clinical laboratory evaluations (hematology, blood chemistry, and urinalysis), adverse event and serious adverse event monitoring, as recorded in the [Assessment schedule](#).

[REDACTED]

[REDACTED]

Figure 3-1 Part A: Effects of Carbohydrate in the Breakfast Meals

Screening Period	Baseline Day -3 to -1	Sequence	Treatment Period 1 Day 1-3	Washout 5 Days	Treatment Period II Day 9-11	Washout 5 Days	Treatment Period III Day 17-19	Washout EOS Day 20-22
Day -28 to -4								
	Run-In	1 (n=8)	50% CHO		25% CHO		0% CHO	
	Run-In	2 (n=8)	25% CHO		0% CHO		50% CHO	
	Run-In	3 (n=8)	0% CHO		50% CHO		25% CHO	

CHO = % carbohydrate content in the standardized breakfast meal

LIK066 50mg QD will be given in the morning immediately before the breakfast meal

Part B: Effects of Supplements (Psyllium and Calcium carbonate)

The same Assessment Schedule will apply to Part B of the study as described for Part A. Each subject will consume one of the three supplement treatment options (6 g psyllium, 1g calcium carbonate (to be provided in a 4mL liquid, sugar free formulation), or no supplement) according to the randomization assignment immediately after administration of 50 mg LIK066, and before having the standardized breakfast meal, containing 50% carbohydrate (Figure 3-2). All supplement products will be the sugar free version.

Treatment Period I (Day 1 to Day 3); Period II (Day 9 to Day 11); Period III (Day 17 to Day 19)

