3.6.1 Blood sample volumes

Approximately 450 mL of blood is planned to be collected over a period of 8 weeks including the Screening visit, from each subject as part of the study. Additional samples for monitoring of any safety findings would be in addition to this. This is not considered to be a risk for this population.

Timings of blood sample collection are outlined in the Assessment Schedule, [Section 8.1](#).

A summary blood log is provided in the Site Operations Manual, together with instructions for all sample collection, processing, storage, and shipment information.

See [Section 8.9](#) regarding the potential use of residual samples.

4 Population

The study population will consist of male and female overweight or obese subjects.

A total of approximately 48 patients will be enrolled in the study and randomized. At least 36 subjects are expected to complete the study.

The investigator must ensure that all subjects meet the subsequent eligibility criteria at screening. No additional criteria should be applied by the investigator to ensure that the study population is representative of all eligible subjects. A relevant record (e.g. checklist) of the eligibility criteria must be stored with the documentation at the study site.

Deviation from any entry criterion excludes a patient from enrollment into the study.

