11.4.4 Sensitivity analyses

As a sensitivity analysis, the interaction between treatment and day will be assessed, and if non-significant, the results from the 3 days will be averaged and corresponding model-based quantities extracted.

Covariates such as baseline number of diarrhea may be included in the model when appropriate.

The model assumption of negative binomial distribution will be examined, especially if over-dispersion (i.e. variance>mean) exists. If the data doesn't fit negative binomial distribution or over-dispersion doesn't exist, other models such as Poisson regression will be explored.

The model assumption of no first-order carry-over effect may be evaluated by incorporating first-order carry-over effects into the above statistical model, and performing a type 3 test for the first-order carry-over effect.

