6.1.3.1 Model checking procedures

Missing data will be assumed to be missing at random and thus the above analysis will be performed on all available data. There will be no imputation of missing data.

The interaction between treatment and day will be assessed, and if non-significant, the results from the 3 days will be averaged and corresponding model-based quantities extracted.

The model assumption of negative binomial distribution will be examined, especially if over-dispersion (i.e. variance>mean) exist. If the data doesn't fit negative binomial distribution or over-dispersion doesn't exist, other models such as Poisson regression will be explored.

The model assumption of no first-order carry-over effect may be evaluated by incorporating first-order carry-over effects into the above statistical models, and performing a type 3 test for the first order carry-over effect. In addition, descriptive summary statistics will also be provided by treatment sequence and visit in order to assess carry-over effect.

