6.2.3 Statistical model, assumptions and hypotheses

[figure not shown]
Three-day total number of stools with a BSC score of 6 or 7 per period will be analyzed by a negative binomial mixed effects model with random effect of subject and fixed effects of period and treatment. Change from baseline in three-day total number of bowel movements per period will be analyzed by a linear mixed effects model with random effect of subject and fixed effects of period, treatment and baseline three-day total number of bowel movements. Secondary endpoints including average stool consistency, PH and weight will be analyzed by a linear mixed effects model with random effect of subject and fixed effects of period, treatment, and baseline measurement. The least-squares mean and associated 80% CI for each treatment, and the estimated mean difference between each treatment, the p-value, and corresponding two-sided 80% CI, will be extracted from the model, and summarized.

[figure not shown]

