6.2.3.1 Model checking procedures

[figure not shown]
The model assumption of no first-order carry-over effect and negative binomial distribution will be examined for three-day total number of stools with a BSC score of 6 or 7 per period and three-day total number of bowel movements per period similarly to the primary endpoint. Missing data will be assumed to be missing at random and thus the above analyses will be performed on all available data. There will be no imputation of missing data.

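### One cyclic Latin square per part makes the carry-over check weak; all six treatment orders would strengthen it at no cost in primary precision (minor point)

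*Protocol*

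**What the plan says.** Protocol section 6.2: "In each part of the study, subjects will be randomized to one of the following 3 treatment sequences in the ratio of 1:1:1". Table 6-1 gives ABC, BCA, CAB in Part A (50%, 25%, 0% carbohydrate) and ADE, DEA, EAD in Part B (no supplement, psyllium, calcium carbonate). Protocol Figures 3-1 and 3-2 and SAP Figures 1-1 and 1-2 show the same sequences.

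On carry-over:
- Protocol 11.4.4 makes the model-based check optional for the primary endpoint: "The model assumption of no first-order carry-over effect may be evaluated by incorporating first-order carry-over effects into the above statistical model". SAP 6.1.3.1 repeats this and adds that "descriptive summary statistics will also be provided by treatment sequence and visit in order to assess carry-over effect".
- SAP 6.2.3.1 is firmer for the secondary totals: "The model assumption of no first-order carry-over effect and negative binomial distribution will be examined for three-day total number of stools". The model being checked has no carry-over term; the count "will be analyzed by a negative binomial mixed effects model with random effect of subject and fixed effects of period and treatment".
- Protocol 11.7 assumes no carry-over in the power simulation.

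Protocol 3.2 argues for two three-period parts and for a five-day washout. It does not say why only these three orders were chosen.

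**The concern.** In Part A, B can follow only A, C only B, and A only C; Part B has the same pattern. In periods 2 and 3 the current treatment therefore fixes the preceding one. Direct and carry-over effects can be separated only because period 1 has no predecessor.

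Two things are at stake. First, the carry-over test has little power, so a non-significant result may be taken as reassurance that it cannot give. Second, if one meal or supplement leaves a residual effect, all of that effect falls on a single successor treatment. In Part B, calcium carbonate is followed only by no supplement, which is the reference for both supplement comparisons.

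**Working it through.** **Inputs.** Sequences from Table 6-1; 24 subjects per part from protocol 3.1; dispersion 1 or 2.4, means 1.5 to 5 and 37.5% drop-out from protocol 11.7; half-life 10-16 h from protocol 1.1. The documents give no ICC, no carry-over size and no level for the carry-over test, so these are assumed below.

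**The plan's own figure.** 5/(1 - 0.375) = 8 per sequence, and 8 x 3 x 2 = 48, as stated. A re-simulation with 15 completers (gamma-Poisson counts, Poisson likelihood conditional on subject in place of the planned SAS procedure) gave 87-91% power at two-sided 0.20, the level matching the 80% intervals. The planned power is not in question here.

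**Precision without carry-over terms.** Each subject receives every treatment and each period contains every treatment equally often. With within-subject variance 1, the variance of a treatment contrast is 2/24 = 0.083 for the cyclic set and for six orders.

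**Precision with carry-over terms.** The model has subject, period, treatment and first-order carry-over (none in period 1). Contrast variance is read from the inverse information matrix.

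| Subject effect | Cyclic, 8 x 3 | Six orders, 4 x 6 |
|---|---|---|
| Fixed | 0.417 (x5.0) | 0.104 (x1.25) |
| Random, ICC 0.3 | 0.315 (x3.8) | 0.102 (x1.23) |
| Random, ICC 0.9 | 0.405 (x4.9) | 0.104 (x1.25) |

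With fixed subjects, the share of treatment information lost to carry-over is 1 - 1/5.0 = 80% for cyclic and 1 - 1/1.25 = 20% for six orders. The protocol's simulation inputs imply a count-scale ICC of mean x k/(1 + mean x k), from 1.5/2.5 = 0.60 to 12/13 = 0.92. At those values the cyclic factor is about 4.4 to 4.9.

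**Count model.** Simulated counts (3 vs 1.5 episodes, dispersion 1 and 2.4, 24 subjects, same conditional likelihood) gave about 5.7- to 6.1-fold for cyclic and 1.4- to 1.5-fold for six orders. The penalty appears somewhat larger for both.

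**Power of the carry-over test.** Assume a residual of 1 within-subject SD from one treatment and none from the others, with fixed subjects. The noncentrality is 1.78 (cyclic) against 7.11 (six orders), on 2 and 42 df. Power is 19% against 63% at level 0.05, and 45% against 86% at level 0.20. Protocol section 4 says "At least 36 subjects are expected to complete the study", that is 18 per part. Power is then 15% against 49% at 0.05, and 39% against 76% at 0.20.

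**Bias if a residual L is ignored.** In the cyclic set, the sole successor receives L in two of its three periods, so its mean rises by 2/3 L. With six orders, each of the two other treatments follows the source half the time, so each rises by 2/3 x 1/2 = 1/3 L.

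| Source (Part A) | Contrast | Cyclic | Six orders |
|---|---|---|---|
| 50% | 25% vs 50% | 0.67L | 0.33L |
| 50% | 0% vs 50% | 0 | 0.33L |
| 25% | 25% vs 50% | 0 | -0.33L |
| 25% | 0% vs 50% | 0.67L | 0 |
| 0% | 25% vs 50% | -0.67L | 0 |
| 0% | 0% vs 50% | -0.67L | -0.33L |

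Part B has the same structure. A residual from calcium carbonate shifts both supplement-vs-none contrasts by -0.67L with the cyclic set; with six orders it shifts calcium-vs-none by -0.33L and psyllium-vs-none by 0.

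**Drug carry-over.** Day 3 to Day 9 is 6 x 24 = 144 h; 144/16 = 9 and 144/10 = 14.4 half-lives.

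**The case against.** The strongest reply is that nothing planned depends on the check. The study is declared non-confirmatory, the primary model has no carry-over terms, no decision rule uses the test, and primary precision is the same under either set of sequences. That stands, and it makes this a minor point.

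Nor is there evidence of carry-over. LIK066 is well washed out by half-life, and a residual common to all treatments is absorbed by period. Only a meal- or supplement-specific residual remains. The documents neither show one nor exclude one, because the washout rationale in protocol 3.2 concerns diarrhea after the last LIK066 dose. The 1-SD residual is illustrative.

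Six orders are also a trade-off. For each source they put 0.33L into one contrast that the cyclic set leaves unbiased, for example 0% vs 50% when the source is 50%. That stands too, although the worst bias is halved.

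Finally, the plan already gives a direct look at residual effects: "During Day -2 through Day 22, daily bowel movements will be monitored and collected". Because sequence identifies the preceding treatment, the by-sequence-and-visit summaries already show Days 8 and 16 by preceding treatment. This helps, but only as support. Those days are off LIK066, so they cannot show a residual that acts only under the drug. Washout diet also differs from the standardised baseline breakfast: "There are no particular restrictions for the meals during the washout time period". Average BSC score is not a substitute: SAP 6.2.1 defines it per 24-hour collection, and Table 8-1 marks none on Days 8 or 16.

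**Conclusion.** The point holds as a cheap design improvement of minor weight. The cyclic sequences make the sponsor's own carry-over check weak: a 5.0-fold variance penalty with fixed subjects (3.8 to 4.9 with random subjects at an assumed ICC of 0.3 to 0.9), against about 1.25 with six orders. The worst bias from an ignored residual is 0.67L against 0.33L. These figures rest on a linear model with one value per period and 24 complete subjects per part; they are only approximate for the negative binomial models.

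A reader might infer more, and the documents do not support it:
- That the primary results or the power are compromised. They are not, since neither involves carry-over terms.
- That carry-over cannot be estimated. It can, but imprecisely.
- That carry-over is present or the washout too short. Nothing in the documents shows this.
- That six orders would make the test strong. In the example above, power stays below 80% at level 0.05.

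**What to change.** **If randomisation has not started.** Randomise to all six orders in each part: add ACB, BAC and CBA in Part A, and AED, DAE and EDA in Part B. Allocate 4 subjects to each (24/6 = 4), in blocks that are multiples of 6. Update Table 6-1, protocol Figures 3-1 and 3-2, and SAP Figures 1-1 and 1-2. N, visits and the analysis model stay the same. The cost is a new randomisation list, three more orders per part for the site, and the 0.33L bias in one contrast per source noted above.

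**If randomisation has started.** This may be the case, because the SAP's document history attributes its September 2017 changes to issues in study conduct. Keep the sequences. State in SAP 6.1.3.1 and 6.2.3.1 that a non-significant carry-over test will not be taken as evidence of no carry-over. Read the bowel movement counts on Days 8 and 16, in the summaries already planned, as supportive evidence only. Do not make those days or average BSC the main check, and do not put the linear-model efficiency figures in the SAP, because the main endpoint is a negative binomial count. The cost is a sentence of text and no new data.

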6.3 Treatment assignment and randomization

Randomized treatment will be assigned to individual subjects by way of a randomization number, which will be in the range of [REDACTED] and [REDACTED] in Part A and Part B, respectively.

The randomization number is only used to identify which treatment the subjects have been randomized to receive. The Subject number assigned to a subject at screening remains the unique identifier for the subject throughout the study. For information on subject numbering, please see 'Subject numbering' section in the SOM.

Replacement randomization numbers will be in the range of [REDACTED] for Part A and [REDACTED] for Part B. If a subject requires a replacement, the replacement subject will be assigned a randomization number corresponding to the original subject (e.g. Subject [REDACTED] would replace Subject [REDACTED]). Any additional subjects enrolled will use sequential subject numbering.

The table below details the general details of the numbering of the subjects once randomized to treatment:

Table 6-2 **Randomization assignment numbering**

Cohort	Randomization numbers	Replacement randomization numbers
Part A (n=24)	[REDACTED]	[REDACTED]
Part B (n=24)	[REDACTED]	[REDACTED]

The randomization numbers will be generated using the following procedure to ensure that treatment assignment is unbiased. Treatment allocation cards will be produced by or under the responsibility of Novartis Drug Supply Management using a validated system that automates the random assignment of treatment arms to randomization numbers in the specified ratio. The randomization scheme for subjects will be reviewed and approved by a member of the Randomization Office.

There will be no stratification of randomization. Block randomization will be used to generate the treatment allocation cards.

Follow the details outlined in the Site Operations Manual regarding the process and timing of treatment assignment and randomization of subjects.

